2 LIST OF ABBREVIATIONS AND DEFINITIONS OF TERMS

Abbreviation	Term
AE	adverse event
BOR	best overall response
CBR	clinical benefit rate
CR	complete response
CRF	case report form
CSR	clinical study report
CTCAE	Common Terminology Criteria for Adverse Events
DCR	disease control rate
DLT	dose-limiting toxicity
DOR	duration of response
Е	Eribulin Mesylate alone
ECG	electrocardiogram
ECOG	Eastern Cooperative Oncology Group
EP	Eribulin Mesylate in combination with PEGylated Recombinant Human Hyaluronidase (PEGPH20)
НА	hyaluronan
HER2	human epidermal growth factor receptor 2
IV	intravenous
MBC	metastatic breast cancer
MedDRA	Medical Dictionary for Regulatory Activities
MSE	musculoskeletal events
NE	not evaluable
NYHA	New York Heart Association
ORR	objective response rate
OS	overall survival
PD	progressive disease
РЕ	pulmonary embolism
PEGPH20	PEGylated recombinant human hyaluronidase
PFS	progression-free survival

Abbreviation	Term
РК	pharmacokinetic
PK/PD	pharmacokinetic/pharmacodynamic
PR	partial response
РТ	preferred term
RECIST 1.1	Response Evaluation Criteria in Solid Tumors (version 1.1)
RP2D	recommended Phase 2 dose
RR	response rate, respiratory rate
SAE	serious adverse event
SAP	Statistical Analysis Plan
SD	stable disease
SOC	system organ class
ТЕ	thromboembolic
TEAE	treatment-emergent adverse event
TNBC	triple negative breast cancer
US	United States
WHO DD	World Health Organization Drug Dictionary

3 INTRODUCTION

The purpose of this statistical analysis plan (SAP) is to describe the procedures and the statistical methods that will be used to analyze and report results for Eisai Protocol E7389-M000-219 (Amendment 01, dated as 27Oct2016). This was an originally planned, Randomized, Open-label, Multicenter, Phase 1b/2 Study of Eribulin Mesylate in Combination with PEGylated Recombinant Human Hyaluronidase (PEGPH20) versus Eribulin Mesylate Alone in Subjects with Human Epidermal Growth Factor Receptor 2 (HER2)-Negative, High-Hyaluronan (HA) Metastatic Breast Cancer (MBC). This study was carried out only for Phase 1b as planned during the study process due to its early termination. Therefore, this SAP is only focused on statiscial methods and analyses that will be performed in the final for the data of Phase 1b, but the information on the original study design (overall for both Phase 1b and Phase 2) is explained first in Section 3.1 for Study Objectives, in Section 5.1 for Study Endpoints.

This SAP will be finalized and approved before the database lock of the study.

3.1 Study Objectives

3.1.1 Primary Objectives

- For the Phase 1b part to determine safety tolerability and recommended Phase 2 dose (RP2D) of eribulin mesylate in combination with PEGPH20 in subjects with HER2-negative MBC previously treated with up to two lines of systemic anticancer therapy in the metastatic setting.
- For the Phase 2 part to evaluate objective response rate (ORR) of eribulin mesylate in combination with PEGPH20 in subjects with HER2-negative, HA-high, MBC previously treated with up to two lines of systemic anticancer therapy in the metastatic setting.

3.1.2 Secondary Objectives

- To evaluate progression-free survival (PFS)
- To evaluate overall survival (OS)
- To evaluate the safety and tolerability

3.1.3 Exploratory Objective(s)

- To explore clinical benefit rate (CBR)
- To explore disease control rate (DCR)
- To explore duration of response (DOR)
- To explore efficacy for subjects enrolled in Phase 1b

- To evaluate exposure-response relationship
- To explore pharmacokinetics of PEGPH20 and eribulin mesylate when coadministered
- To identify and explore tumor and blood markers (e.g. Plasma HA levels) that correlate with clinical outcomes, including efficacy

3.2 Overall Study Design and Plan

This was a randomized, open-label, multicenter, Phase 1b/2 study of eribulin mesylate in combination with PEGPH20 versus eribulin mesylate alone in subjects with HER2-negative, HA-high, MBC previously treated with up to two lines of systemic anti-cancer therapy (cytotoxic drugs or targeted anti-cancer agents) in the metastatic setting. CDK4/6 inhibitors and mTOR inhibitors would not be considered as prior lines of therapy. Any single agents or combination of scheduled pre-planned treatments (given concomitantly, sequentially, or both) would be considered as one regimen. Hormonal therapy and bone metastases treatment (eg, bisphosphonates, denosumab, etc) would not be considered forms of systemic anti-cancer therapy.

3.2.1 Phase 1b and Phase 2

Study Phase 1b would occur in two parts (Part 1 and Part 2 ("Expansion Part")):

Part 1: would conduct run-in safety cohorts (dose levels 1, 0, and -1, as necessary) of 6 subjects each, until RP2D to be determined as followed:

- The part 1 would have dose-limiting toxicity (DLT) assessed in the first cycle, and would include at least 1 initial safety run-in cohort in which the first 6 enrolled subjects (with any hyaluronan [HA] level) would receive PEGPH20 at a dose of 3 µg/kg intravenously (IV) on Days -1 and 7 of a 21-day cycle, each dose followed approximately 24 (±4) hours later with eribulin mesylate 1.4 mg/m2 IV on Days 1 and 8 (dose level 1).
- Dose level 1 could be selected as the RP2D if no more than 1 subject had a DLT; otherwise, a second cohort of 6 subjects would receive a lower dose of PEGPH20 at 1.6 μg/kg on Days -1 and 7, each dose followed approximately 24 (±4) hours later with eribulin mesylate 1.4 mg/m2 IV on Days 1 and 8 (dose level 0).
- Dose level 0 could be selected as the RP2D if no more than 1 subject of this second cohort had a DLT; otherwise, a third cohort of 6 subjects would receive PEGPH20 1.6 μ g/kg on Days -1 and 7, each dose followed approximately 24 (±4) hours later with eribulin mesylate at a lowered dose of 1.1 mg/m2 IV on Days 1 and 8 (dose level 1).
- If no more than 1 of 6 subjects in this third cohort had a DLT, the Phase 2 part would proceed with dose level -1 as the RP2D. Otherwise, alternative doses would be explored prior to the start of Phase 2.

3.2.2 Study Drugs Administration

On Days -1 and 7 of each 21-day cycle, Phase 1b subjects and Phase 2 (Arm A, only) subjects would receive PEGPH20 via IV injection over 10 minutes, approximately 1 mL/minute (a window of +2 minutes would be allowed, ie, infusion could be 10 to 12 minutes). On the following day, approximately 24 (\pm 4) hours after Day -1 and Day 7 doses of PEGPH20, eribulin mesylate via IV injection over 2 to 5 minutes would be administered. Phase 2 subjects in Arm B would receive eribulin mesylate alone on Day 1 and Day 8 of each 21-day cycle.

For the subjects of Phase 1b and Phase 2 Arm A, dexamethasone 8 mg twice daily would be administered orally in each treatment cycle to alleviate musculoskeletal toxicities. Subjects would take dexamethasone orally within 2 hours prior to the beginning of each PEGPH20 and 8 to 12 hours after the completion of the infusions. The investigator might adjust the dose of dexamethasone based on the clinical presentation of each subject.

3.2.3 Subject Study Phases

For subjects in the study there would be the following three study phases:

• The Pre-treatment phase: consisted of the 21-day Screening Period and Baseline Period. The Baseline Period would include the Baseline Visit (all subjects),

performed on or before designated Study Day -2 or C1D-1, prior to administration of their first dose of PEGPH20 (see Schedule of Procedures/Assessments, Table 7 in Protocol).

- Treatment phase: would begin with the first dose of study drug administration in Cycle 1 and would continue in 21-day cycles until completion of the End of Treatment visit (within 30 days of the last study drug administration) or subject discontinuation of study, whichever occurred first. In the presence of clinical benefit, subjects would remain on study treatment until unacceptable toxicity (excluding Thromboembolic (TE) events which required discontinuation of PEGPH20 yet subjects might continue on eribulin mesylate alone), or disease progression occurred, or the subject withdrew consent.
- Follow-up phase: would start at the End of Treatment visit and would continue as long as the subject was alive or until the subject withdrew consent or lost to follow-up. Subjects who discontinued study treatment before disease progression would continue to undergo disease assessment every 6 weeks ±1 week until documentation of disease progression or start of another anticancer therapy. Follow-up assessment for survival would be performed every 12 weeks ±1 week.

3.2.4 Tumor, Safety and PK Assessments

Tumor assessments would be performed every 6 ± 1 weeks from the date of first dose of study drugs or sooner if clinically indicated, until documentation of disease progression. In subjects who discontinued study therapy without documented disease progression, every effort would be made to continue monitoring their disease status by radiologic imaging every 6 weeks, until (1) the start of new anticancer treatment, (2) disease progression (3) death, or (4) the end of the study, or withdrawal of consent, whichever occurred first.

Pharmacokinetic (PK) assessments of eribulin mesylate and PEGPH20 would be performed for all 12 subjects in the Phase 1b Expansion Part. Only subjects receiving combination treatment with PEGPH20 and eribulin mesylate (Arm A) in the Phase 2 part would undergo sparse PK sampling for population pharmacokinetic/pharmacodynamic (PK/PD) analysis, where feasible.

Safety assessments would be by monitoring and recording of all adverse events (AEs), including all CTCAE v4.03 grades (both increasing and decreasing severity) and serious AEs (SAEs), regular monitoring of hematology, and clinical chemistry, urinalysis, regular measurement of vital signs, 12-lead ECGs, and ECOG and detail schedules would be found in protocol Table 7 (Schedule of Procedures/Assessments).

4 DETERMINATION OF SAMPLE SIZE

The sample size calculation was based on the comparisons of the primary endpoint ORR. Assuming $ORR_{EP} = 0.35$ and $ORR_E = 0.15$, forty evaluable subjects per arm would provide a power of 0.800 in testing of ORR_{EP} vs ORR_E when using normal approximation to binomial

test with a one-sided significance of 0.10. Up to 114 subjects would be enrolled in the trial, comprising of up to 30 in the Phase 1b part (6 to 18 in the safety run-in cohort plus 12 in the Expansion part) and 84 in the Phase 2 part (to obtain 80 evaluable subjects).

5 STATISTICAL METHODS

5.1 Study Endpoints

In this study, all the primary, secondary, and exploratory endpoints on tumor related measurement/definition would be from the investigator assessment per RECIST 1.1.

5.1.1 Primary Endpoints

- The primary endpoint of Phase 1b was the RP2D of the eribulin mesylate and PEGPH20 combination.
- The primary efficacy endpoint of Phase 2 was ORR defined as the proportion of subjects who had a best overall response (BOR) of complete response (CR) or partial response (PR).

5.1.2 Secondary Endpoints (Phase 2)

- Progression-Free Survival (PFS) defined as the time from date of randomization to date of first documentation of disease progression or death, whichever occurred first
- Overall Survival (OS) defined as the time from the date of randomization until date of death from any cause

5.1.3 Exploratory Endpoints (Phase 2)

- Clinical Benefit Rate (CBR) was the proportion of subjects who had a BOR of CR or PR or durable stable disease (SD). Stable disease must be maintained at ≥ 23 weeks after randomization to be considered durable SD, and any stable disease required at least 1 post-treatment assessment that met the SD criteria ≥5 weeks after the start of treatment (Phase 1b) or randomization (Phase 2).
- Disease Control Rate (DCR) was the proportion of subjects who had a BOR of CR, PR, or SD.
- Duration of Response (DOR) was defined as the time from the date that the criteria were met for CR or PR (whichever was recorded first) to the date that progressive disease (PD) was objectively documented or death, whichever occurred first.

5.2 Study Subjects

5.2.1 Definitions of Analysis Sets

- DLT Evaluable Set will include subjects enrolled in Phase 1b who completed the first treatment cycle (ie, took at least 2 doses of eribulin mesylate and PEGPH20 with no more than 1 dose reduction) and had sufficient safety evaluation. This will be the analysis set for DLT evaluation in the Phase 1b Part 1 of the study.
- Safety Analysis Set will include subjects who received at least 1 dose of the study drug. This will be the analysis set for both safety and efficacy evaluations.
- Pharmacokinetic (PK) Analysis Set will include all eribulin mesylate and PEGPH20treated subjects with at least 1 quantifiable eribulin concentration with a documented related dosing history. This will be the analysis set for PK data.

Enrolled subjects will also be considered in the final, and they are the subjects who signed the informed consent form.

5.2.2 Subject Disposition

The number (percentage) of subjects enrolled (ie, signed informed consent form), treated, discontinued from study/treatment (with reasons according to the categories in the CRF) will be summarized. The study status at the end of study or data cutoff will be summarized using the data from the survival follow-ups. The data will be listed as well.

5.2.3 Protocol Deviations

Major protocol deviation criteria will be established and subjects with major protocol deviations will be identified and reviewed before the database lock. Major protocol deviations by each category will be summarized. The data will be listed as well.

5.2.4 Demographic and Other Baseline Characteristics

Demographic and other baseline characteristics will be summarized. Continuous demographic and baseline variables will include age, weight, height, BMI (BMI (kg/m2) = Weight in Kilograms / (Height in Meters)²), and BSA; categorical variables will include sex, age group (<65, \geq 65 years), race, race group (White and Non-White), ethnicity, geographic region, enrollment strata (Triple Negative Breast Cancer, Other HER2 negative Metastatic Breast Cancer), estrogen status, progesterone status, Eastern Cooperative Oncology Group (ECOG) Performance Status, New York Heart Association (NYHA) classification, and pregnancy test. The data will be listed as well.

Medical History

The number (percentage) of subjects reporting a history of any medical condition and current medical condition, as recorded on the CRF, will be summarized. Medical History will be

coded using MedDRA (version 19.1 or newer), and summarized by System Organ Class (SOC) and Preferred term (PT). The data will be listed as well.

Disease History

Disease history and characteristics data at study entry will be summarized as recorded on eCRF. The data will be listed as well.

5.2.5 Prior and Concomitant Therapy

All investigator terms (verbatim terms) for medications recorded in the CRF will be coded to an 11-digit code using the World Health Organization Drug Dictionary (WHO DD). The number (percentage) of subjects who took prior and concomitant medications will be summarized by Anatomical Therapeutic Chemical (ATC) class and WHO DD preferred term.

Prior medications will be defined as medications that stopped before the first dose of study drug. Concomitant medications will be defined as medications that (1) started before the first dose of any study drugs and were continuing at the time of the first dose of any study drugs, or (2) started on or after the date of the first dose of any study drugs up to 28 days after the subject's last dose. Medications that cannot be determined to be prior/concomitant/post-treatment due to missing or incomplete dates will be regarded as concomitant.

Previous anti-cancer medications and previous anti-cancer procedures will be summarized similarly. Previous radiotherapies will also be summarized per the CRF data category.

The data summarized will be listed as well.

5.2.6 Treatment Compliance

Dose modifications (i.e., reduction and missing) will be summarized (see Section 5.6.1).

5.3 Data Analysis General Considerations

5.3.1 Pooling of Centers

Data from all centers will be pooled in analyses.

5.3.2 Adjustments for Covariates

Not applicable.

5.3.3 Multiple Comparisons/Multiplicity

Not applicable.

5.3.4 Examination of Subgroups

No subgroup analyses will be performed.

5.3.5 Handling of Missing Data, Dropouts, and Outliers

Rules of handling full/partial missing dates and the censoring rules for PFS are explained in Section 8. Handling missing data in analyses of ORR, CBR and DCR is explained in Section 5.4. Any potential outlier values will be investigated and they will be analyzed as originally reported in the locked database.

5.3.6 Other Considerations

No other consideration.

5.4 Efficacy Analyses

All the efficacy endpoints defined in the protocol for Phase 2 (in Section 5.1), except OS and the duration of response, will be summarized for Phase 1b data. Their definitions will use the first date of any study drugs instead of the date of randomization, and the BOR will be determined from the confirmed CR or PR (after 28 days starting at the initial CR or PR observed) per RECIST 1.1.

In the efficacy analyses,

- Number (percentage) of subjects involved in objective response rate (CR or PR), disease control rate (CR, PR or SD), clinical benefit rate (CR, PR or durable SD), and durable SD rate will be reported together with their 95% confidence intervals (using the exact method of binomial distribution). Each BOR category will also be summarized in number (percentage) of subjects. In the analyses of ORR, CBR and DCR, subjects with missing data will be considered as non-responders and will be included in the denominator when calculating ORR, CBR and DCR. The figure of percent change of sum of target lesions' diameters from baseline and the figure of subjects' timepoint overall responses will be presented as well. The data and the tumor timepoint assessments (on target lesions, non-target lesions) from the CRF will be listed as well.
- The Kaplan-Meier (KM) estimated PFS (month) at median, Q1 and Q3, and the KM estimated rates of PFS at the timepoints of 3, 6 and 12 months will be reported together with their 95% confidence intervals (the methods of generalized Brookmeyer and Crowley for survivals and Greenwood Formula for rates). The KM estimated PFS will also be plotted. The censoring rules for PFS calculation are explained in Section 8. The data will be listed as well.

Available PK data will be summarized, plotted and listed.

No pharmacodynamic, pharmacogenomic, and other biomarker data will be available.

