8.5 Censoring Rule

Table 2 shows the primary censoring rules for the derivation of PFS based upon investigator's tumor assessment and the Food and Drug Administration (FDA) "Guidance for Industry Clinical Trial Endpoints for the Approval of Cancer Drugs and Biologics (2007)".

No.	Situation	Date of Progression or Censoring	Outcome
1	No baseline tumor assessments	Date of the first dose	Censored
2	Progression documented between scheduled visits	Date of first radiologic PD assessment	Progressed
3	No progression at the time of data cut-off or withdrawal from study	Date of last adequate radiologic assessment prior to or on date of data cut-off or withdrawal from study	Censored
4	New anti-cancer treatment started	Date of last adequate radiologic assessment prior to or on date of new anti-cancer treatment	Censored
5	Death before first PD assessment	Date of death	Progressed
6	Death between adequate assessment visits*	Date of death	Progressed
7	Death or progression after two or more missed visit**	Date of last adequate radiologic assessment before missed tumor assessments	Censored
2	No post-baseline tumor assessments but known to be alive	Date of the first dose	Censored

 Table 2Censoring Rules for Analysis of Progression-Free Survival

CR = complete response, PD = progressive disease, PR = partial response, SD = stable disease,

* Adequate tumor assessment is a radiologic assessment of CR, PR, SD, non-CR/non-PD or PD as determined by investigators.

** More than two missed visits is defined if the duration between the last tumor assessment and death or PD is longer than 84 days (12 weeks) for subjects on the every 6 week scanning schedule during treatment /follow up phase in this study:

The priority of the censoring rules is as follows:

- 1. If the subject had PD or death, the following sequence will be applied:
 - If a subject did not have baseline tumor assessment (No. 1), the subject will be censored on date of the first dose. However, if the subject died or had clinical progression within 84 days (12 weeks) after the first dose and did not receive new anti-cancer treatment, the date of death or clinical progression will be the PFS event date (not censored).
 - If a subject had new anti-cancer treatment before PD or death (No. 4), the subject will be censored on the date of the last tumor assessment prior to or on the date of new anti-cancer treatment.

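### SAP 5.1.3 and 5.4 count stable disease still ongoing at a cut-off before week 23 as a clinical-benefit failure, so CBR and the durable SD rate can only be biased downward or not at all

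*SAP*

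**What the plan says.** Four parts of the SAP bear on this.

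- **Definition.** Section 5.1.3: "Stable disease must be maintained at ≥ 23 weeks after randomization to be considered durable SD". For Phase 1b, Section 5.4 moves the starting point: "Their definitions will use the first date of any study drugs instead of the date of randomization".
- **Estimator.** Section 5.4 gives ORR, DCR, CBR and the durable SD rate as percentages; the "durable SD rate will be reported together with their 95% confidence intervals (using the exact method of binomial distribution". Section 5.2.1 makes the Safety Analysis Set, meaning everyone with at least one dose, the efficacy set. Section 8.1 reports by dose level.
- **Missing data.** Section 5.4: "subjects with missing data will be considered as non-responders and will be included in the denominator when calculating ORR, CBR and DCR". The sentence does not name the durable SD rate and does not mention SD that is ongoing at a cut-off.
- **PFS.** In Section 8.5, Table 2 No. 3, the situation "No progression at the time of data cut-off or withdrawal from study" is censored at the last adequate radiologic assessment.

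The Introduction (Section 3) gives the setting: "This study was carried out only for Phase 1b as planned during the study process due to its early termination". Section 5.2.2 and Table 2 refer to a data cut-off, but neither document gives its date or a minimum follow-up before it.

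**The concern.** CBR and the durable SD rate depend on reaching a fixed time point. Take a subject with SD at weeks 6 and 12 whose observation stops administratively at week 15. That subject has not failed; the time point was never reached. Under the definition and the all-treated denominator, the result is nonetheless the same as for a subject who progressed at week 12. PFS treats the same stop as censoring.

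CBR and the durable SD rate are among the few efficacy results that the terminated study will report. If some subjects were cut off early, the two rates mix drug effect with date of enrolment, and a reader of the table could not tell which was at work. The confidence interval gives no warning, because it measures sampling error in the observed proportion and not misclassification of immature subjects.

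**Working it through.** The documents state no CBR or durable SD target, power or result, so there is no planned figure to reproduce. The check has two parts.

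**1. What happens to an immature subject**

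- Section 3.2.4 sets the scans: "Tumor assessments would be performed every 6 ± 1 weeks from the date of first dose of study drugs". The third scan falls at 18 ± 1 weeks, that is, weeks 17 to 19. The fourth falls at 24 ± 1 weeks, that is, weeks 23 to 25. The fourth is therefore the first scheduled scan that can show SD at 23 weeks or later.
- If observation ends before then with SD ongoing, the definition in 5.1.3 is not met, so the subject is not in the numerator.
- Under 5.2.1 the subject is in the denominator.
- Nothing in 5.4 sets such a subject apart: there is no minimum follow-up, separate category or sensitivity analysis. Section 5.3.5 sends missing-data handling for CBR back to 5.4.

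The failure count thus follows from the definition and the denominator together. The missing-data sentence alone does not establish it. DCR is not affected once SD at 5 weeks or later has been documented.

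**2. How much it can matter**

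Let n be the number treated at a dose level, x the number with observed clinical benefit, m the number with SD ongoing at a cut-off before week 23, and q the chance that such a subject would have gone on to qualify. The reported rate is x/n. The expected rate with full follow-up is (x + mq)/n, so the shift is −mq/n. It is never upward, and it is at most 1/n per affected subject:

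- n = 18 (planned total at the RP2D, SAP 3.2.1): 1/18 = 5.6 points
- n = 6 (one run-in cohort): 1/6 = 16.7 points

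Illustration with n = 18 and an assumed x = 6. The values of x and m are assumptions, not data.

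| m | As planned, x/n | Immature excluded, x/(n − m) | All would have qualified, (x + m)/n |
|---|---|---|---|
| 0 | 33.3% | 33.3% | 33.3% |
| 1 | 33.3% | 6/17 = 35.3% | 7/18 = 38.9% |
| 2 | 33.3% | 6/16 = 37.5% | 8/18 = 44.4% |
| 3 | 33.3% | 6/15 = 40.0% | 9/18 = 50.0% |
| 4 | 33.3% | 6/14 = 42.9% | 10/18 = 55.6% |

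The planned estimate and its exact 95% CI (13.3% to 59.0%) are the same in every row. With q from 0.25 to 1, the expected shift is 1.4 to 5.6 points for m = 1 and 4.2 to 16.7 points for m = 3.

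**The case against.** The strongest reply is that no bias has been shown. A reader might infer from the early termination that the two rates *are* biased downward. The documents do not support that. They say that Phase 2 was not run; they give no cut-off date, no follow-up times and no affected subject. If every Phase 1b subject was followed to progression or past week 23, the effect is zero. This stands, and it is why the point is limited to direction and a per-subject bound.

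A reader might also take Section 3.2.4 to mean that all scanning stopped when the study ended. The limit "4) the end of the study, or withdrawal of consent, whichever occurred first" sits in the sentence on subjects who stopped therapy without documented progression. For the others, scanning runs until progression. The exposure therefore comes from whatever data cut-off or study end applied, and its timing is unknown.

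Nor can the share of immature subjects be projected from the planning figures. The 114 subjects over about 24 months are a whole-study average that includes 84 Phase 2 subjects. The 8 months is an estimated median treatment duration, not a PFS median. The ORR of 0.35 is the Phase 2 assumption for HA-high disease, whereas the run-in took any HA level. Any projection from these would be purely hypothetical.

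The stakes are modest. CBR is exploratory, with no test or decision rule. Section 5.4 also plans a figure of each subject's time-point responses, full listings, and Kaplan-Meier PFS rates at 3, 6 and 12 months, so a careful reader could find immature subjects. CBR and PFS need not agree in any case, because CBR counts a response of any duration. All of this stands, but none of it puts the number of immature subjects beside the rate that it affects.

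The defence that counting missing data as failure is a disclosed, conservative convention stands only in part. It suits withdrawal and loss to follow-up, which may reflect treatment failure. An administrative stop is not a subject outcome.

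**Conclusion.** The gap is real and cheap to close. As the SAP is written, SD ongoing at a cut-off before week 23 counts against CBR and the durable SD rate, while PFS censors the same subject. Any resulting bias is downward or nil, and is bounded by 1/n per affected subject: 5.6 points at n = 18 and 16.7 points at n = 6. The number affected, which may be zero, cannot be determined from the documents, so no overall size can be given. The bounds use planned group sizes; the number actually treated at each dose level is not stated. No test or decision rule depends on these rates, so this is a recommended improvement and not a flaw that undermines the study.

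**What to change.** Amend SAP 5.4 before database lock:

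1. Keep the all-treated CBR and durable SD rate as planned. Label them as lower bounds if any subject is immature.
2. Report, by dose level, the number with *SD ongoing at cut-off, less than 23 weeks*.
3. Add supplementary CBR and durable SD rates for subjects whose first dose was at least 25 weeks before the cut-off (the week-24 scan plus its 1-week window). Select on dosing date only, never on outcome. Within this group, withdrawal, missing scans and loss to follow-up still count as failures.
4. Add week 23 to the Kaplan-Meier PFS time points (161 days, or 161/30.4375 = 5.3 months by the SAP 8.4 conversion), so that an estimate which censors the immature subjects stands at the same horizon.

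The cost is some SAP wording and additional table entries; no new data are needed. The downside is a smaller denominator and a wider exact CI for the supplementary rates, which will be felt at a dose level of 6. Selecting on dosing date also sets aside recently dosed subjects whose outcome is already known, whether early progression or SD documented at week 23 or 24. That is the price of not selecting on outcome, and those subjects remain in the all-treated rates. If every subject had at least 25 weeks before the cut-off, the two sets of figures coincide and nothing is lost.
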